### 3.7 Pharmacokinetic-Pharmacodynamic Assessments

Scatterplots of PK parameters ( $C_{max}$ , AUCs, etc.) and GCSI-DD scores with BT  $T_{1/2}$  (change from baseline) may be created, as may other plots for other plasma concentration and/or PK parameters with select safety measures, prolactin data, and/or measures of gastric emptying time and symptoms of gastroparesis.

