predispositions, or in patients who were also receiving other QT-prolonging drugs or potent cytochrome P450 (CYP) 3A4 inhibitors, such as ketoconazole. However, there have been reports of cases of QT prolongation among patients taking domperidone with none of these additional risk factors. The potential for QT prolongation is believed to be related to increased plasma concentrations of domperidone. It is suggested that the mean effect on QT of  $\geq 10$  msec (the definition of QT prolongation) may occur when the domperidone plasma concentration reaches approximately 65 ng/mL. Therefore, limiting the maximum plasma concentration ( $C_{max}$ ) of domperidone to approximately 60 ng/mL may significantly lower the risk of QT prolongation.

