As noted previously, domperidone has been associated with prolongation of the QT interval on electrocardiograms (ECGs). During postmarketing surveillance, there have been very rare cases ( $<1/10,000$  cases) of QT prolongation and QT prolongation-induced Torsades de pointes in patients taking oral domperidone. These reports included patients with confounding risk factors, electrolyte abnormalities, and concomitant treatment, which may have been contributing factors. Epidemiological studies showed that domperidone was associated with an increased risk of serious ventricular arrhythmias or sudden cardiac death. A higher risk was observed with IV administration and following oral administration in patients older than 60 years, patients taking total daily oral doses greater than 30 mg, and patients concurrently taking QT-prolonging drugs or CYP3A4 inhibitors. However, there have been reports of cases of QT prolongation in patients taking domperidone with none of these additional risk factors. From a review of the literature, including an assessment of the thorough QT and case-controlled studies with respect to the incidence of QT prolongation and sudden cardiac death, the data appear to indicate that the risk of QT prolongation is related to the increased plasma levels of domperidone. Additionally, the FDA Expanded Access to Investigational Drugs program website for requesting domperidone indicates that the serious risks associated with domperidone are related to domperidone levels in the blood, and higher domperidone blood levels are associated with higher risk of these events.

Other study-related risks include those associated with blood draws, such as discomfort, bruising, infection, bleeding, pain, redness at the puncture site, and/or lightheadedness, as well as temporary

discomfort, redness, or rash at the site of ECG electrode placement, and dizziness, headache, stomach discomfort, or fainting due to fasting.

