The doses planned for inclusion in this study were chosen based upon the safety, tolerability, and PK profile established in the Phase 1 SAD and MAD studies. The mean  $C_{\max}$  of 48.18 ng/mL observed in healthy subjects receiving 60 mg BID (the highest proposed dosing regimen for the current study) is below the highest observed mean  $C_{\max}$  from the 120 mg single dose (96.8 ng/mL), a dose that was well-tolerated by healthy subjects with no clinically meaningful QT prolongation. Given the association of QT prolongation and domperidone, subjects participating in this study will be monitored closely for adverse events, including those that have been reported with domperidone, and 12-lead ECGs will be collected at each visit to the clinic.

A goal of this study is to assess the effect of CIN-102 on gastric emptying in subjects with idiopathic or diabetic gastroparesis. Given the known antiemetic and prokinetic effects of domperidone, it is possible that subjects may experience improvement in their symptoms during the course of this study.

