### **2.2 Exploratory Objectives**

The exploratory objectives of this study include the following:

- To assess the effect of multiple doses of CIN-102 on nausea associated with gastroparesis based on the nausea score on the American Neurogastroenterology and Motility Society Gastroparesis Cardinal Symptom Index Daily Diary (ANMS GCSI-DD)
- To assess the effect of multiple doses of CIN-102 on ANMS GCSI-DD scores (total and subscales) in subjects with idiopathic or diabetic gastroparesis
- To assess the effect of multiple doses of CIN-102 on a variety of patient reported outcomes
- To characterize exposure-response relationships of CIN-102

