14. On Days 1 and 14 ( $\pm 2$  days), ECGs will be performed prior to the morning dose and [REDACTED] hours (as applicable) after the morning dose and should be completed  $\pm 15$  minutes from the specified timepoints. For subjects participating in the intensive PK, additional ECGs will be performed at [REDACTED] (if applicable) after the morning dose). Note: if collection of specific individual PK samples (including but not limited to the samples at [REDACTED] for the intense PK subgroup) are not required based on written Sponsor approval, the final ECGs for these visits must be collected when the final PK sample is obtained. See [Appendix C](#) for ECG review criteria guidance.
15. Subjects will have baseline GEBT performed between Days -10 and -3 after a minimum 14-day washout from motility agents and on Day 14 ( $\pm 2$  days) 30 minutes after study drug administration. Subjects will fast for a minimum of 8 hours before the breath test. Breath samples will be obtained twice prior to consumption of a standardized,  $^{13}\text{C}$ -enriched meal and then on Day 1 at 45, 90, 120, 150, 180, and 240 minutes post-meal an 8-hour fast on Days -10 to -3 and on Day 14 ( $\pm 2$  days) at 45, 90, 120, 150, 180, and 240 minutes starting 30 minutes after study drug administration. Fasting glucose will be assessed before GEBT to ensure a blood glucose level of  $\leq 275$  mg/dL.
16. [REDACTED]  
[REDACTED]  
[REDACTED]  
[REDACTED]  
[REDACTED]
17. Sample collected predose. The Day 1 prolactin sample is not required to be repeated if a prolactin was obtained for the pre-randomization visit in the last 72 hours.
18. Study drug will be dispensed with treatment assigned via IRT on Day 1.
19. All subjects will take a dose of blinded study drug (CIN-102 or placebo capsules) orally at [REDACTED] AM [REDACTED] and [REDACTED] PM [REDACTED]  
[REDACTED]  
[REDACTED]  
[REDACTED]  
[REDACTED]  
[REDACTED]  
[REDACTED]  
[REDACTED]  
[REDACTED]

- The evening dose will be self-administered by the subject. If a subject reports vomiting during the treatment period, subjects should attempt to note the time of vomiting in relation to time of study drug administration and report this to site staff during scheduled clinic visits.
20. Study drug accountability will occur on Days 3, 7, 10, and 14 or on Early Termination if applicable. Unused study drug will only be collected on Day 14 ( $\pm 2$  days) or on Early Termination if applicable.

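### No estimate of QTcF change at a given concentration is specified: SAP 3.7 turns the protocol's conditional PK-safety correlation into optional plots that do not name QTcF

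*SAP*

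**What the plan says.** **Rationale.** Protocol 1.1 says of domperidone: "The potential for QT prolongation is believed to be related to increased plasma concentrations of domperidone". It adds that a mean QT effect of at least 10 msec "may occur when the domperidone plasma concentration reaches approximately 65 ng/mL", and that holding the Cmax "of domperidone to approximately 60 ng/mL may significantly lower the risk of QT prolongation". Protocol 1.4 repeats the link: "the data appear to indicate that the risk of QT prolongation is related to the increased plasma levels of domperidone". That section supports the highest regimen by its mean Cmax, "of 48.18 ng/mL observed in healthy subjects receiving 60 mg BID". It compares this with 96.8 ng/mL after a single 120 mg dose of CIN-102, at which no clinically meaningful QT prolongation was seen.

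**Objective and use.** Protocol 2.2 and SAP 2.1 list as an exploratory objective "To characterize exposure-response relationships of CIN-102". Protocol 1.3 says the results are to inform dose selection in later studies.

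**Data.** Protocol Appendix A, Table 2, schedules triplicate ECGs and PK samples at the same visits: before and after dosing on Days 1 and 14, with a predose PK sample on Days 3, 7 and 10, and again on Day 15 or 16. Most clock times are redacted.

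**Analysis.** Protocol 9.2.1.5 says that, if the data allow, correlation of concentrations or PK parameters with selected safety measures will be attempted. SAP 3.7 names optional scatterplots of PK parameters and GCSI-DD scores against change in BT T1/2, then adds "as may other plots for other plasma concentration and/or PK parameters with select safety measures". SAP 3.9.4 averages the triplicates, summarises ECG parameters by treatment group and timepoint, plots mean QTcF, and counts four QTcF alert criteria.

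**The concern.** The plan has a stated hypothesis that concentration drives QT risk, an exposure-response objective, and ECGs and plasma samples taken at the same visits. What it lacks is an analysis that joins them. In going from protocol to SAP, a conditional commitment became a permission, and QTcF is not among the measures named.

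Summaries by arm answer a different question. They describe the average QTcF at a dose and time, not the change expected at a concentration, and neither document plans a placebo-corrected QTcF change or an interval even by arm. If exposure varies between subjects on one regimen, an arm mean mixes low and high concentrations. At stake is what the study can say about QTcF at the exposures it reaches, which is relevant to the dose selection it is meant to support. If a model is chosen only after the QTcF data are seen, its result will also carry less weight.

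**Working it through.** **1. The provisions side by side**

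| Place | Commitment | QTcF named? | Estimate at a concentration? |
|---|---|---|---|
| Protocol 9.2.1.5 | attempt at correlation, if data permit | no | no |
| Protocol 9.2.2 | QTcF plots by treatment and time, if applicable | yes | no |
| SAP 3.7 | optional plots | no | no |
| SAP 3.9.4 | summaries by arm and time, threshold counts | yes | no |

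All four sections are legible, so the gap does not come from redaction. A correlation, even if carried out, would not give a QTcF change in msec at a stated concentration.

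**2. Sample size.** 3 cohorts × (15 active + 5 placebo) = 60, that is 45 active and 15 placebo. This reproduces SAP 2.2.7. No SD, margin, alpha or power is stated, so there is no further figure to reproduce.

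**3. What the protocol's own figure would imply.** Assume a straight line through zero and take 10 msec at 65 ng/mL. The slope is 10/65 = 0.154 msec per ng/mL.
- At 48.18 ng/mL: 7.4 msec
- At 60 ng/mL: 9.2 msec
- At 96.8 ng/mL: 14.9 msec

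The 65 ng/mL figure is for domperidone. The last value sits uneasily with the report in Protocol 1.4 for CIN-102 at a mean Cmax of 96.8 ng/mL. The relation may therefore not carry over, and the planned tables would not estimate it either way.

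**4. What an arm mean could hide.** The documents give no coefficient of variation for Cmax, so I assume a lognormal Cmax with mean 48.18 ng/mL and CV 30-50%.

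σ² = ln(1 + CV²), μ = ln(48.18) − σ²/2, P(Cmax > 65) = 1 − Φ((ln 65 − μ)/σ).

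For CV 30%: σ = 0.2936, μ = 3.8319, z = (4.1744 − 3.8319)/0.2936 = 1.167, so P = 12.2%. For CV 40% it is 16.6% and for CV 50% 19.2%.

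**5. What a model would add in precision.** Take one ECG-PK pair per subject and an assumed SD of QTcF change of 8-15 msec.

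By dose, 15 v 15: 90% half-width = t(0.95, 28) × SD × √(2/15). For SD 8: 1.701 × 8 × 0.365 = 5.0 msec.

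Model on 60 subjects with intercept, active-treatment indicator and concentration (0 for placebo): half-width = t(0.95, 57) × SD × √(L′(X′X)⁻¹L), with L = (0, 1, 48.18). This was averaged over simulated concentrations with Cmax CV 30% or 50%. The two lower arms were assumed to reach 1/6 and 1/3, or 1/3 and 2/3, of the top exposure.

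| Assumed SD (msec) | By dose | Model at 48.18 ng/mL |
|---|---|---|
| 8 | 5.0 | 4.3-4.7 |
| 10 | 6.2 | 5.4-5.9 |
| 12 | 7.5 | 6.5-7.1 |
| 15 | 9.3 | 8.1-8.9 |

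At SD 8 the narrowing is 1 − 4.7/5.0 = 6% to 1 − 4.3/5.0 = 14%. An estimate of 7.4 msec (step 3) would have an interval excluding zero at SD 8-12 but not at SD 15.

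**The case against.** **Phase and style of the plan.** This is a Phase 2A proof-of-concept study without a formal sample size calculation, and even the primary GEBT endpoint is only summarised. A mixed model for one safety measure goes beyond the rest of the SAP. This stands as a limit on weight. It does not remove the mismatch between Protocol 9.2.1.5 and SAP 3.7, or the fact that exposure-response is a listed objective.

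**Other QT handling.** A reader might infer that individual QTcF is ignored. It is not. SAP 3.9.4 counts subject-level exceedances and SAP 3.9 lists ECG data. Protocol 3.3.1 and 3.3.2 set individual QTcF criteria, and the review committee includes a cardiologist and a clinical pharmacologist. The gap concerns estimation, not monitoring.

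**Later modelling.** A reader might infer that the effect will never be estimated. The documents do not bar it, and Protocol 5.3 mentions modelling or simulation when it describes how PK data are de-identified. They specify none for QTcF.

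**Precision.** A reader might expect a large gain from a model that uses several times per subject. Most of that gain comes from the repeated times, not from concentration. With four times per subject and assumed between- and within-subject SDs of 5 and 6 msec, the SE of a 15 v 15 contrast falls from √((25 + 36) × 2/15) = 2.85 to √((25 + 36/4) × 2/15) = 2.13 msec by averaging alone. With SDs of 8 and 8 it falls from 4.13 to 3.27. The averaged contrast is a time-averaged effect rather than one at peak, but the point stands.

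**Time-matching.** Exact pairing is partly inferred. The Table 2 footnote that "the final ECGs for these visits must be collected when the final PK sample is obtained" applies when PK samples are waived and concerns only the last ECG. ECG windows are ±15 minutes, while the PK windows in SAP 3.6.3 are ±2 or ±5 minutes. A pairing rule is therefore needed.

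**Conclusion.** The point holds as a protocol-SAP gap in an exploratory safety analysis, with a cheap remedy. No estimate of QTcF change at a given concentration is specified in either document, although the protocol treats concentration as the driver of domperidone QT risk and collects ECGs and PK samples at the same visits. The primary analysis is unaffected.

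In size, the benefit is mainly that a prespecified, interpretable estimate with an interval would exist. The gain in precision is modest, about 6-14% in half-width at an assumed SD of 8 msec. The 12-19% share above 65 ng/mL rests wholly on an assumed Cmax CV of 30-50%.

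Two stronger readings lack support. One is that CIN-102 carries an established QT harm at these exposures: the 60-65 ng/mL figures are for domperidone, and Protocol 1.4 reports no clinically meaningful prolongation with CIN-102 at a mean Cmax of 96.8 ng/mL. The other is that the plan itself regards analysis by dose as the inferior scale: it never ranks the two.

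**What to change.** In SAP 3.7, replace the optional plot, as far as QTcF is concerned, with a prespecified exploratory linear mixed model:

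- **Outcome:** change from baseline in QTcF, using the triplicate mean and the baseline of SAP 3.9.4, on time-matched ECG-PK pairs with a stated pairing window.
- **Fixed effects:** concentration (0 for placebo), treatment indicator, nominal time, baseline QTcF.
- **Random effects:** subject intercept, with a random slope only if the model converges.
- **Placebo:** state that placebo is pooled for this model and name the analysis set. SAP 3.2 pools placebo for safety but not for PK analyses, and the PK Population excludes placebo subjects, so the current text leaves this unclear.
- **Report:** the slope, and the predicted placebo-corrected QTcF change with 90% CI at each arm's observed geometric mean Cmax. Report it at 60-65 ng/mL only if such concentrations are observed.
- **Checks:** non-linearity, and delay between concentration and effect.

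The cost is SAP wording and one model on data already collected. The downside is reliance on a linear, no-delay relation, which must be checked with a limited sample. No dose or clinical rule changes.

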### 3.8 Pharmacogenomics (PGx) Assessment

A single, optional PGx blood sample may be collected at any time during the subject's participation in the study and will be the collection data will be listed for the ITT Population. The PGx samples may be used for genetic research to explore the underlying causes of variability and/or differences in response in PK, PD, and/or safety data following administration of CIN-102. Any analysis of these samples will be detailed in a separate document.

### 3.9 Safety Assessments

Safety data, including adverse events, physical examinations, ECGs, vital sign assessments, and clinical laboratory evaluations (including prolactin), will be summarized and listed for the Safety Population by treatment group and time of collection, when appropriate (see protocol Appendix A: Schedule of Procedures for collection timing).

#### 3.9.1 Adverse Events

AEs will be captured from the date of informed consent through study completion. All AEs will be coded to system organ class and preferred term by using MedDRA version 22.0. Treatment-emergent adverse events (TEAEs) are defined as AEs that start after the first dose of study drug.

An overview of AEs will be provided including counts and percentages of subjects (and event counts for any TEAEs) with the following:

- Subjects with any AEs

- Subjects with any TEAEs (overall and by maximum severity)
- Subjects with any study drug related TEAEs (overall and by maximum severity)
- Subjects with any treatment-emergent serious AEs
- Subjects with any Drug-Related treatment-emergent serious AEs
- Subjects with any AEs leading to death
- Subjects with any TEAEs leading to discontinuation
- Subjects with any Drug-Related TEAEs leading to discontinuation

Counts and percentages of subjects (and event counts for any TEAEs) will also be presented by system organ class and preferred term for each of the categories in the overview.

Listings will be presented specifically for SAEs and TEAEs leading to discontinuation of study drug, as well as all AEs.

### 3.9.2 Clinical Laboratory Tests

Safety laboratory tests will include chemistry, hematology, coagulation, prolactin, and urinalysis (see protocol Appendix B: Clinical Laboratory Analytes for complete list of tests).

#### 3.9.2.1 Chemistry, Hematology, Coagulation, Urinalysis

Continuous safety laboratory data (values and change from baseline) will be summarized by treatment group at baseline and at each post-baseline time point. Categorical data will be summarized using frequency counts and percentages by treatment group at baseline and post-baseline scheduled visits.

Shift tables describing post-baseline out-of-normal range shifts will be provided for continuous laboratory results.

Data will also be listed.

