#### **3.3.1 Criteria for Temporary Suspension of Dosing**

Dosing within a cohort or between cohorts will be temporarily suspended until a full cumulative data review is complete if any of the following occur:

- Any study drug-related SAE grade 3 or higher based on Common Terminology Criteria for Adverse Events (CTCAE) Version 5.0
- Any single subject whose ECG (average triplicate ECGs as interpreted by central read) demonstrates a heart-rate corrected QTcF interval (QTcF) >500 msec or in whom there is an increase in QTcF >60 msec from baseline (confirmed by repeat ECG)
- Any new ECG abnormality deemed clinically significant by the investigator
- Any study drug-related cardiac adverse event. In the event that a subject experiences a vasovagal or near-syncopal episode, dosing within a cohort or subsequent cohort may proceed as planned unless the episode is associated with ECG abnormality or the event is deemed to be severe in intensity (severity) by the Investigator
- A study drug-related adverse event from a single System Organ Class deemed to be of moderate intensity (severity) in 4 or more subjects

- Any of the following laboratory abnormalities that are thought to be study drug-related or in which an alternative explanation is not reasonable:
  - ALT or AST  $>8 \times$  the upper limit of normal (ULN), or
  - ALT or AST  $>5 \times$  ULN and persist for more than 2 weeks, or
  - ALT or AST  $>3 \times$  ULN in conjunction with elevated total bilirubin  $>2 \times$  ULN or international normalized ratio  $>1.5$ , or
  - ALT or AST  $>3 \times$  ULN with appearance of fatigue, nausea, vomiting, right upper quadrant pain or tenderness, fever, rash, and/or eosinophilia ( $>5\%$ )
- Any single subject who develops serious study drug-related electrolyte abnormalities due to vomiting and/or inability to maintain adequate oral hydration that impacts cardiac stability
- Other conditions as deemed medically appropriate based on the Investigator's judgement

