#### **4.2 Exclusion Criteria**

Patients who meet any of the following criteria will be excluded from participation in the study:

1. Has a history of, or current, clinically significant arrhythmias as judged by the Investigator, including ventricular tachycardia, ventricular fibrillation, and Torsades de pointes. Patients with minor forms of ectopy (eg, premature atrial contractions) are not necessarily excluded, per Investigator discretion.
2. Has clinically significant bradycardia with a resting heart rate under 50 beats per minute, sinus node dysfunction, or heart block.
3. Has prolonged heart rate-corrected QT interval using Fridericia's formula (QTcF) (QTcF >450 msec for males or QTcF >470 msec for females) based on the average of triplicate ECGs.
4. Has a personal or family history of long QT syndrome, Torsades de pointes, or other complex ventricular arrhythmias or family history of sudden death.
5. Has evidence (based on screening or baseline assessments) or history of clinically significant immunologic, hematologic, renal, endocrine, pulmonary, GI, cardiovascular, hepatic, psychiatric, neurologic, or allergic disease (including drug allergies); surgical conditions; cancer (with the exception of basal or squamous cell carcinoma of the skin and cancer that resolved or has been in remission for >5 years prior to the Screening Visit); or any condition that, in the Investigator's opinion, might significantly interfere with the absorption, distribution, metabolism, or excretion of the study drug.  
Note: Cholecystectomy and appendectomy are allowed.
6. Has a history of prolactin-releasing pituitary tumor (ie, prolactinoma).
7. Has elevated serum prolactin.

Note: Patients who are on medications that are known to increase prolactin (eg, domperidone, metoclopramide, phenothiazines, SSRIs, verapamil, etc) with an elevated prolactin at the time of screening may be considered for this study.

8. Has known or suspected hypogonadism, current clinically significant menstrual abnormalities (eg, oligomenorrhea or amenorrhea), gynecomastia, galactorrhea, or other clinical features that in the Investigator's opinion may be consistent with hyperprolactinemia.
9. Has pyloric injection of botulinum toxin within 6 months of screening and/or during the course of the study.

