10. Has bilirubin, alkaline phosphatase, aspartate aminotransferase (AST), or alanine aminotransferase (ALT) levels greater than  $2 \times$  the upper limit of normal or has a Child-Pugh classification grade of B or C.
11. Has a serum creatinine level greater than  $1.5 \times$  the upper limit of normal or has an estimated glomerular filtration rate (eGFR)  $<30$  mL/min/1.73 m^2 using the Chronic Kidney Disease Epidemiology Collaboration (CKD-EPI) equation at screening.
12. Has a hemoglobin level  $<10$  g/dL at screening.
13. Has thyroid-stimulating hormone (TSH) levels that are abnormal at screening, as judged by the Investigator.
14. Has inability to perform a breath test.
15. Has known allergy to eggs or spirulina.
16. Use of investigational, prescription, or over-the-counter medications as follows:
  - Actively participating in an experimental therapy study; received experimental therapy with a small molecule within 30 days of randomization or 5 half-lives (whichever is longer); or received experimental therapy with a large molecule within 90 days of randomization or 5 half-lives, (whichever is longer).

- [REDACTED]
  - [REDACTED]
  - [REDACTED]
  - [REDACTED]
  - [REDACTED]
  - [REDACTED]
17. History of alcoholism or drug abuse within 2 years prior to dosing as defined by the Diagnostic and Statistical Manual of Mental Disorders, 4th Edition.
18. Typical consumption of  $\geq 14$  alcoholic drinks weekly.

19. Evidence of ongoing illicit drug use.
20. Positive for human immunodeficiency virus (HIV) antibody, hepatitis C virus (HCV) by RNA, or hepatitis B surface antigen (HBsAg) at the Screening Visit.
21. Donated blood or blood products within 30 days prior to dosing.
22. Currently undergoing treatment with weight loss medication or prior weight loss surgery (eg, gastric bypass surgery).
23. Pregnant, breastfeeding, or planning to become pregnant during the course of study.
24. Inability to swallow medication.
25. Currently receiving parenteral feeding or presence of a nasogastric or other enteral tube (eg, percutaneous endoscopic gastrostomy [PEG] tube) for feeding or decompression.
26. Known or suspected gastric outlet obstruction (eg, peptic stricture) or other GI mechanical obstruction as documented by upper GI tract endoscopy or upper GI radiographic series in the past 3 years.
27. Known history or current diagnosis of intestinal malabsorption or pancreatic exocrine disease.

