### **4.3 Randomization Criteria**

In addition to the general criteria listed in [Sections 4.1](#) and [4.2](#), in order to be randomized into the study, subjects must also meet the following criteria at the time of randomization:

- Continues to satisfy all inclusion/exclusion criteria.
- Has been off all motility agents and antiemetics for at least 14 days and is willing to remain off such medications (except for protocol-specified antiemetic rescue medication) during the course of the study.

- Demonstrates a confirmed diagnosis of idiopathic or diabetic gastroparesis as defined by the following:
  - Current upper GI symptoms (eg, nausea/vomiting, postprandial fullness, early satiety, bloating, and/or epigastric/ abdominal pain).
  - Documented DGE within the 10 days prior to first dose of study drug based on GEBT using  $^{13}\text{C}$ -spirulina platensis demonstrating  $T_{1/2} > 80$  minutes. Subjects with a  $T_{1/2} > 200$  minutes may be considered for the study with sponsor approval.

[REDACTED]

[REDACTED]

[REDACTED]

[REDACTED]

[REDACTED]

[REDACTED]

[REDACTED]

[REDACTED]

- Has continued required results of the initial safety laboratory test performed at Screening.

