#### 9.2.2 Analysis of Safety

Safety data, including physical examinations, ECGs, vital sign assessments, clinical laboratory evaluations (including prolactin), and adverse events, will be summarized by treatment group and time of collection, when appropriate. Individual and mean time course of absolute prolactin values and change from baseline prolactin by treatment may also be generated.

Descriptive statistics (arithmetic mean, standard deviation, median, minimum, and maximum) will be calculated for quantitative safety data, as well as for the difference from baseline, when appropriate. Absolute and change from baseline values in QT (using QTcF) will be plotted against timepoints by treatment, if applicable. The central overread ECG data will be utilized for all safety assessments and analyses.

Shift tables describing out-of-normal range shifts will be provided for clinical laboratory results.

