#### 3.9.2.2 Prolactin

Prolactin values, change from baseline, and percent change from baseline will be summarized by treatment group at baseline and at each post-baseline time point. A shift table of post-baseline out-of-normal shifts will also be presented. All prolactin data will be listed.

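### The normal-range shift table cannot show worsening in subjects who enter above the upper limit of normal, and no planned table counts subjects by arm at the plan's own hepatic limits

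*SAP*

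**What the plan says.** **Planned laboratory outputs.** SAP section 3.9.2.1 summarizes values and change from baseline by arm and time point. Under SAP section 3.1.4 that means n, mean, median, standard deviation, minimum and maximum. The categorical output for continuous analytes is: "Shift tables describing post-baseline out-of-normal range shifts will be provided for continuous laboratory results". SAP section 3.9.2.2 adds percent change for prolactin and then: "A shift table of post-baseline out-of-normal shifts will also be presented". Protocol section 9.2.2 agrees: "Shift tables describing out-of-normal range shifts will be provided for clinical laboratory results". None of these places mentions ULN multiples, grades or fold change. All laboratory data are listed.

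**Who may enter.** Exclusion criterion 10 (protocol section 4.2) removes subjects for bilirubin, alkaline phosphatase, AST or ALT only at "levels greater than $2 \times$ the upper limit of normal", apart from a Child-Pugh limit. Criterion 11 removes them for creatinine only above 1.5 x ULN or eGFR below 30. Protocol section 4.3 requires at randomization that the subject "Continues to satisfy all inclusion/exclusion criteria"; it does not require these analytes to be in range. Criterion 7 excludes elevated prolactin, but its note says that subjects on prolactin-raising medication "with an elevated prolactin at the time of screening may be considered for this study". Baseline is the last pre-dose value (SAP section 3.1.3).

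**The plan's hepatic limits.** Protocol section 3.3.1, repeated in SAP section 2.2.3.1, lists suspension criteria under "Any of the following laboratory abnormalities that are thought to be study drug-related or in which an alternative explanation is not reasonable". They are ALT or AST >8 x ULN; >5 x ULN lasting more than 2 weeks; >3 x ULN with bilirubin >2 x ULN or INR >1.5; and >3 x ULN with listed symptoms or eosinophilia.

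**The contrast.** SAP section 3.9.4 takes the QTcF thresholds from protocol Appendix C and summarizes them by treatment group, including a percent-increase category.

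**The concern.** A low/normal/high shift table registers a subject only when a value crosses a reference limit. A subject already above ULN at baseline has no upper limit left to cross, so any further rise stays in the High-to-High cell beside subjects who stayed put. A trivial move from 0.98 to 1.02 x ULN, by contrast, counts as a shift.

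This matters here because the entry criteria allow High baselines on the liver tests, and because the plan states its hepatic concerns in ULN multiples. Safety and tolerability is the first-listed objective. A reader of the report will want to know how many subjects per arm exceeded 3, 5 or 8 x ULN, and whether any had transaminases and bilirubin raised together. The planned summaries do not answer either question directly.

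**Working it through.** The documents state no shift count, prevalence or power figure on this point, so there is nothing to reproduce. The check classifies values against the reference range, with High meaning above 1 x ULN.

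**1. A 4-fold rise from various baselines (post = 4 x baseline)**

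| Baseline (x ULN) | Post (x ULN) | Normal-range table | Table at <=1, >1-3, >3-5, >5-8, >8 |
|---|---|---|---|
| 0.5 | 2.0 | Normal to High: shift | <=1 to >1-3 |
| 1.0 | 4.0 | Normal to High: shift | <=1 to >3-5 |
| 1.01 | 4.04 | High to High: no shift | >1-3 to >3-5 |
| 1.25 | 5.0 | High to High: no shift | >1-3 to >3-5 |
| 1.5 | 6.0 | High to High: no shift | >1-3 to >5-8 |
| 2.0 | 8.0 | High to High: no shift | >1-3 to >5-8 |

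From any admitted baseline above 1 and up to 2 x ULN, a 4-fold rise ends above 4 and up to 8 x ULN. That is always over the 3 x ULN level, and over 5 x ULN when baseline exceeds 5/4 = 1.25. It is never a crossing. The 0.5 to 2.0 rise counts as a shift and the 2.0 to 8.0 rise does not.

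**2. Distance from the entry limit to the plan's levels.** From 2 x ULN, the 3, 5 and 8 x ULN levels are reached at 3/2 = 1.5-, 5/2 = 2.5- and 8/2 = 4-fold. A value of exactly 8 x ULN reaches but does not exceed the >8 limit.

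**3. A worked subject.** ALT from 1.8 to 7.0 x ULN is a 7.0/1.8 = 3.9-fold rise, a change of 5.2 x ULN.
- Shift table: High to High, no shift.
- Arm mean change (n = 15): 5.2/15 = +0.35 x ULN.
- By-visit maximum: 7.0 x ULN for the value and 5.2 x ULN for the change, provided no other subject is higher and the value falls at a summarized visit.
- Count of subjects above 3 or 5 x ULN by arm: not planned.
- Same-subject pairing with bilirubin: not planned, because each analyte is summarized separately.

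**4. How many subjects could be affected.** The share *h* entering above ULN on a given analyte is not in the documents. It is assumed here, with subjects independent:

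| Assumed *h* | Expected per arm, 15*h* | P(at least one in arm) = 1 - (1 - *h*)^15 |
|---|---|---|
| 5% | 0.75 | 54% |
| 10% | 1.5 | 79% |
| 20% | 3 | 96% |
| 30% | 4.5 | 99.5% |

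The last column is the chance that an arm contains a subject who cannot register an upward shift. It is not the chance that a rise is missed, which would also need a multi-fold rise in that same subject. The documents give no basis for estimating that.

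**The case against.** The strongest reply is that the rise would not be lost. The continuous summaries include maxima of both value and change. Protocol section 8.1 asks for clinically significant abnormalities that are present at first dose and significantly worsen to be reported as adverse events; these are CTCAE-graded and tabulated by arm and maximum severity. The suspension criteria prompt a cumulative data review. Everything is listed. The SAP's shift table also conforms to protocol section 9.2.2, the ULN limits are operational rules rather than tabulation categories, and the table shells are in a separate document that might add more.

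Much of this stands, and it rules out several stronger readings that a reader might infer:
- *The mean is the only aggregate trace, or the tolerability conclusion rests on listings.* SAP section 3.1.4 supplies the median and maximum, and adverse event tables are planned.
- *The prolactin table will saturate and the doses cannot be told apart.* Percent change by arm is planned and addresses magnitude directly, and no figure in the documents supports saturation. The elevated-prolactin exception covers only medicated subjects at screening, and motility agents and antiemetics must be stopped for at least 14 days before randomization. Baseline may therefore differ from screening.
- *HbA1c is affected because values up to 11% are admitted.* It is scheduled at Screening only, so there is no post-baseline shift to hide.

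The reply leaves a gap. A per-visit maximum gives neither the number of subjects over a limit nor their baseline. Adverse event reporting of a laboratory value depends on intervention, action with study drug, or the investigator's opinion. SAP section 3.1.2 assigns scheduled visits to analysis visits but does not say how unscheduled repeats enter the summaries, although protocol sections 8.1 and 8.6 expect repeats after abnormal results. Unseen shells may fill the gap, but the SAP text does not require them to.

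**Conclusion.** The point holds as a gap in the categorical summary. For subjects with a baseline above ULN, which the entry criteria permit, the normal-range shift table cannot separate worsening from no change, and no planned output gives by-arm counts at the hepatic limits or pairs ALT/AST with bilirubin within a subject. That follows from the definitions and needs no assumption. How many subjects it touches does: 0.75 to 4.5 of 15 per arm over an assumed 5% to 30%. It does not undermine the safety analysis as a whole, since other outputs may reveal the same rise. It is a specific improvement worth making, and the SAP's handling of QTcF already sets the precedent.

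**What to change.** In SAP section 3.9.2.1, keep the shift table and add one by-arm table of each subject's worst post-baseline value, drawn from scheduled, unscheduled and Early Termination samples:
- ALT and AST in ULN multiples: <=1, >1-3, >3-5, >5-8, >8.
- Total bilirubin: <=1, >1-2, >2 x ULN.
- Count of subjects with ALT or AST >3 x ULN together with bilirubin >2 x ULN.
- All of these shown separately for baseline <=1 and >1 x ULN.

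The cut-points are those of protocol section 3.3.1, plus 1 x ULN. The table does not try to reproduce that section's duration, INR or symptom conditions. Creatinine and alkaline phosphatase may be shown in ULN multiples in the same way. In SAP section 3.9.2.2, a table of worst prolactin value in ULN multiples, split by normal or elevated baseline, is optional and would supplement the planned percent-change summary.

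The cost is a few lines of SAP text and one table shell (a second if the prolactin option is taken), with no new data. The downside is one extra table that will be mostly sparse at 15 subjects per arm.
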